4.5.13 Samples for Clinical Repository

All residual samples (or leftover biologic samples after protocol-defined studies are completed) obtained during the study (FFPE, fresh-frozen, plasma, etc.) will be stored in an academic central repository. The specimens in the study repository will be made available for future biomarker research towards further understanding of treatment with GDC-0032, of breast cancer, related diseases, and adverse events, and for the development of potential, associated diagnostic assays. The implementation of study repository specimens is governed by the Study Steering Committee, with guidance from a dedicated Translational Research Committee to ensure the appropriate use of the study specimens.

All biomarker specimens will be retained for new research related to this study and/or disease in accordance with the recommendations and approval of the Study Steering

Committee. Samples will be only destroyed if required by local laws relating to the collection, storage, and destruction of biological specimens.

Specimens will be stored up to 15 years or until they are exhausted. The storage period will be in accordance with the institutional review board/ethics committee (IRB/EC)-approved ICF and applicable laws (e.g., health authority requirements).

The dynamic biomarker specimens will be subject to the confidentiality standards described in [Section 8.4](#). The genetic biomarker specimens will undergo additional processes to ensure confidentiality, as described below.

4.5.13.1 Confidentiality

Patient medical information associated with biologic specimens is confidential and may only be disclosed to third parties as permitted by the ICF (or separate authorization for use and disclosure of personal health information) signed by the patient, unless permitted or required by law.

Data derived from biologic specimen analysis on individual patients will generally not be provided to study investigators unless a request for research use is granted. The aggregate results of any research conducted using biologic specimens will be available in accordance with the effective Translational Research Committee policy on study data publication.

4.6 PATIENT, TREATMENT, STUDY, AND SITE DISCONTINUATION

4.6.1 Patient Discontinuation

Patients have the right to voluntarily withdraw from the study at any time for any reason. In addition, the investigator has the right to withdraw a patient from the study at any time. Reasons for withdrawal from the study may include, but are not limited to, the following:

- Patient withdrawal of consent at any time
- Any medical condition that the investigator or Sponsor determines may jeopardize the patient's safety if he or she continues in the study
- Investigator or Sponsor determines it is in the best interest of the patient
- Patient non-compliance

Every effort should be made to obtain information on patients who withdraw from the study. The primary reason for withdrawal from the study should be documented on the appropriate eCRF. However, patients will not be followed for any reason after consent has been withdrawn. Patients who withdraw from the study will not be replaced.

4.6.2 Study Treatment Discontinuation

Patients must discontinue study treatment if they experience any of the following:

- Pregnancy

- Disease progression
- Unacceptable toxicity

The primary reason for study treatment discontinuation should be documented on the appropriate eCRF. Patients who discontinue study treatment prematurely will not be replaced.

4.6.3 Conditions for Terminating the Study

Both the Sponsor and the investigator reserve the right to terminate their participation in the study under the circumstances agreed upon in the site agreement. Should this be necessary, both parties will arrange the procedures on an individual basis after review and consultation. In terminating the study, the Sponsor and investigator will assure that adequate consideration is given to the protection of the patients' interest.

5. ASSESSMENT OF SAFETY

5.1 SAFETY PLAN

GDC-0032 is not approved and is currently in early clinical development. Thus, the entire safety profile is not known at this time. Human experience is currently limited. The following information is based on results from ongoing clinical studies. The safety plan for this study is designed to ensure patient safety and will include specific eligibility criteria and monitoring assessments as detailed below.

Safety will be evaluated in this study through the monitoring of all serious and non-serious adverse events, and laboratory abnormalities (see [Section 5.3.5.3](#)), defined and graded according to NCI CTCAE v4.0. General safety assessments will include serial interval histories, physical examinations, and specific laboratory studies, including serum chemistry and blood counts. All serious adverse events and non-serious adverse events of special interest will be reported in an expedited fashion, via fax to Austrian Breast and Colorectal Cancer Study Group (ABCSG) safety department and also captured in the electronic data capture (EDC) system. In addition, the Sponsor and the investigators will review and evaluate observed adverse events on a regular basis.

All adverse events will be recorded during the trial and for 30 days after the last dose of study treatment or until the end of study visit, whichever occurs later. Patients who have an ongoing study treatment-related adverse event upon study completion or at discontinuation from the study will be followed until the event has resolved to baseline grade, the event is assessed by the investigator as stable, new anti-tumor treatment is initiated, the patient is lost to follow-up, the patient withdraws consent, or it has been determined that study treatment or participation is not the cause of the adverse event.

All adverse events should be attributed by the investigator to study drug or to another clearly identified etiology by the investigator (see [Table 10](#)).

Specific potential safety issues anticipated in this trial, as well as measures intended to avoid, minimize, and manage such toxicities, are outlined in the following sections.

See [Section 5](#) (Assessment of Safety) for complete details of the safety evaluation for this study.

5.1.1 Management of Specific Adverse Events of GDC-0032

Guidelines for management of specific adverse events are outlined in [Table 1](#). Additional guidelines are provided in the subsections below.

Due to the approximately 40-hour half-life for GDC-0032, investigators should consider holding GDC-0032 for certain Grade 2 toxicities until the adverse event resolves to Grade \leq 1 as discussed below (e.g., stomatitis/mucositis, colitis, rash, diarrhea, pneumonitis). Certain toxicities can occur within 1–2 weeks of holding or discontinuing GDC-0032 drug (e.g., pneumonitis, colitis, rash). In these cases, the adverse event eventually resolves. Investigators should follow management guidelines and dose modifications for toxicities as described below, including administration of topical or systemic corticosteroids as appropriate.

Table 1 Overall Dose Modification Guideline for GDC – 0032-Related Adverse Events

GDC-0032	
Starting dose	6 mg at 5 days on / 2 days off
First reduction	3 mg at 5 days on / 2 days off
Second reduction	3 mg at 3 days on / 4 days off ^a
^a If the patient continues to experience specified drug-related adverse events after the second dose reduction, the treatment should be discontinued.	

5.1.1.1 Management of Hyperglycemia

Hyperglycemia has been observed in patients who received GDC-0032 in the single-agent Phase I study.

Patients with diabetes requiring daily anti-hyperglycemic medication or who have a fasting blood glucose level $>$ 125 mg/dL will be excluded from the study. HbA_{1c} and fasting glucose levels will be monitored at baseline, and additional monitoring of fasting glucose levels during the study will be implemented, as outlined in the schedule of assessments. Patients should be instructed to report symptoms associated with hyperglycemia such as thirst, frequent urination, and blurred vision.

Metformin is the first antihyperglycemic medication of choice because of the lower risk of hypoglycemia with this agent. Because metformin in some patients may also cause diarrhea and not be well tolerated, other antihyperglycemic medications such as sulfonylureas (e.g., glimepiride, glipizide) can be used. Extra caution should be used

with other drugs such as sulfonylureas because of the increased risk for hypoglycemia with these agents. Consultation with an endocrinologist can be helpful in managing hyperglycemia.

Specific dose modification and management guidelines for hyperglycemia are provided in Table 2.

Table 2 Dose Modification and Management Guidelines for Hyperglycemia (Based on Fasting Blood Glucose)

Grade	Dose Modification and Management Guidelines for Hyperglycemia (based on fasting blood glucose)
Grade 2	Initiation of an anti-hyperglycemic agent (e.g., metformin) and additional glucose monitoring will be implemented. Dosing with GDC-0032 may either be held or continued per investigator evaluation.
Grade 3 (asymptomatic)	GDC-0032 dosing will be suspended and the patient will be managed as per standard of care, including implementation of additional glucose monitoring and initiation of, or an increase in, the dose of an anti-hyperglycemic therapy (e.g., metformin). If the hyperglycemic event does not improve to Grade ≤ 1 within 28 days, GDC-0032 will be permanently discontinued. If the hyperglycemic event improves to Grade ≤ 1 within 28 days, GDC-0032 dosing may resume at one dose level lower, with approval by the Medical Monitor.
Grade 3 (symptomatic) ^a , Grade 3 (requiring hospitalization), or Grade 4	GDC-0032 dosing will be suspended, and the patient will be managed as per standard of care, including implementation of additional glucose monitoring and initiation of, or an increase in, the dose of anti-hyperglycemic therapy. If the hyperglycemic event does not improve to Grade ≤ 1 within 28 days, GDC-0032 will be permanently discontinued. If the hyperglycemic event improves to Grade ≤ 1 within 28 days, GDC-0032 dosing may resume at one dose level lower, with approval by the Medical Monitor.

^a For example, blurred vision, frequent urination, excessive thirst.

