4.3.2 Dosage, Administration, and Compliance

4.3.2.1 GDC-0032 and Placebo

Patients will receive an oral, daily dose of 6 mg GDC-0032 or placebo on a schedule of 5 days on/2 days off for a maximum of 16 weeks. Patients will take GDC-0032 at the same time of day \pm 2 hours, unless otherwise instructed. Patients will be instructed as to the number of tablets to take. Patients will be asked to record the time and date that they take each dose in a medication diary.

Unless otherwise instructed, GDC-0032 or placebo should be taken on an empty stomach (i.e., approximately 1 hour before or 2 hours after a meal).

If a patient misses a GDC-0032 or placebo dose or vomits up a tablet, she should be instructed to skip that dose and to resume dosing with the next scheduled dose. Missed doses will not be made up. Patients will be instructed to bring their medication diary to

each study visit for assessment of compliance. Patients will also be instructed to bring all unused tablets to each study visit for GDC-0032 or placebo accountability.

Guidelines for dosage modification and treatment interruption or discontinuation are provided in [Section 5.1](#).

Any overdose or incorrect administration of study drug should be noted on the Study Drug Administration eCRF. Adverse events associated with an overdose or incorrect administration of study drug should be recorded on the Adverse Event eCRF.

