5.2.3 Non-Serious Adverse Events of Special Interest (Immediately Reportable to ABCSG)

Non-serious adverse events of special interest are required to be reported by the investigator to ABCSG safety department immediately (i.e., no more than 24 hours after learning of the event; see [Section 5.4.2](#) for reporting instructions). Adverse events of special interest for this study include the following:

- Grade 4 hyperglycemia
- Grade \geq 3 symptomatic hyperglycemia
- Grade \geq 2 colitis or enterocolitis
- Grade \geq 3 diarrhea
- Grade \geq 3 rash
- Grade \geq 2 pneumonitis

- Cases of potential drug-induced liver injury that include an elevated ALT or AST in combination with either an elevated bilirubin or clinical jaundice, as defined by Hy's law (see [Section 5.3.5.5](#))
- Suspected transmission of an infectious agent by the study drug

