Appendix 1 Schedule of Assessments (cont.)

Study procedures	Screening	Treatment Phase						Surgery ^{a,f}	Post Surgery
		W1	W3	W5	W9	W13	W16 (Presurgical Visit)	W17–W18 (Surgery)	4 Weeks (+1W) from Surgery
Days	-28 to -1	1	15 (+2)	29 (±2)	57 (±2)	85 (±2)	106–112	113–126	
Fasting serum chemistry ^j	x	x		x	x	x	x		x
Glycosylated hemoglobin (Hb _{A1c})	x								
Fasting insulin and glucose ^k	x	x		x	x	x	x		x
Fasting lipid profile and amylase ^l	x			x		x	x		x
Coagulation (INR and aPTT)	x			x	x	x	x		x
Urinalysis (laboratory) ^m	x			x	x		x		x
Blood sample for plasma protein biomarkers ⁿ		x			x		x		
Blood sample for ctDNA ^o		x			x		x		
Blood sample for NGS ^p		x							
Pharmacogenomic sample ^q		x							
Concomitant medication ^r	x	x	x	x	x	x	x		x
Adverse events	x	x	x	x	x	x	x		x
Inclusion/exclusion criteria ^s	x								
Visit with breast surgeon (may occur from Week 13)						x			
Surgery ^t								x	
Randomization	x								
Letrozole accountability/dispensation		x	x	x	x	x	x		

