Appendix 1 Schedule of Assessments (cont.)

Study procedures	Screening	Treatment Phase						Surgery ^{a,g}	Post Surgery
		W1	W3	W5	W9	W13	W16 (Presurgical Visit)	W17–W18 (Surgery)	4 Weeks (+1W) from Surgery
Days	-28 to -1	1	15 (+2)	29 (±2)	57 (±2)	85 (±2)	106–112	113–126	
GDC-0032/placebo accountability/ dispensation		x	x	x	x	x	x		
Patient-reported outcomes ^u		x		x	x	x	x		x
Pharmacokinetic sample (see Appendix 2)		x	x		x				

aPTT=activated partial thromboplastin time; CA-125=cancer antigen 125; CTCs=circulating tumor cells; ctDNA=circulating tumor DNA; ECG=electrocardiogram; ECOG=Eastern Cooperative Oncology Group; INR=international normalized ratio; MRI=magnetic resonance imaging; NGS=next-generation sequencing.

Note: All assessments should be performed before dosing, unless otherwise stated. Some assessments may be performed outside the window indicated to accommodate holidays, unforeseen scheduling issues, or ongoing safety issues with the trial and the patient, after approval by the Medical Monitor.

^a Perform within 28 days prior to Day 1 of Cycle 1. Signed informed consent must be provided prior to any study-specific evaluations. Assessments performed as standard of care within the timeframe may be used.

^b Medical history includes clinically significant diseases that are currently active or that were active within the last 5 years, surgeries, cancer history (including date of diagnosis, primary tumor histology, grade, staging, prior cancer therapies, and procedures), reproductive status, smoking history, use of alcohol and drugs of abuse. Demographic data include age, sex, and self-reported race/ethnicity.

^c A complete physical examination should include an evaluation of the head, eyes, ears, nose, and throat, and the cardiovascular, dermatological, musculoskeletal, respiratory, gastrointestinal, genitourinary, and neurological systems as well as weight (in kilograms) and height (in centimeters; height is measured at the screening visit only). Perform symptom-directed physical examination after baseline assessment.

^d Vital signs include measurements of heart rate, respiratory rate, and systolic and diastolic blood pressure while the patient is in a seated position and temperature. Oxygen saturation is obtained by pulse oximetry after the patient has been in a seated position for ≥ 5 minutes. Obtain vital signs predose.

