Appendix 1 Schedule of Assessments (cont.)

- ^g MRI evaluation is optional at Week 9. MRI is mandatory at Week 9 in the event that disease progression is suspected, or if the primary lesion is not evaluable by ultrasound at baseline. Send all scans to the central reading facility for evaluation.
- ^h Two formalin-fixed, paraffin-embedded core needle biopsies and one freshly frozen OCT core needle biopsy are required prior to initiation of treatment (pretreatment) and also on Day 15. A formalin-fixed, paraffin-embedded tumor block from a surgical resection is required at surgery (Weeks 17–18).
- ⁱ Complete blood count includes red blood cell count, hemoglobin, hematocrit, white blood cell count with differential (neutrophils, bands, eosinophils, basophils, lymphocytes, monocytes, and other cells), and platelet count. Screening results may be valid for Week 1, Day 1 if performed within 7 days prior to Week 1, Day 1.
- ^j Fasting (≥ 10 -hour fast) serum chemistry: BUN, creatinine, sodium, potassium, magnesium, bicarbonate, calcium, phosphorus, total protein, albumin, serum bilirubin, alkaline phosphatase, glucose, AST, and ALT. Screening results may be valid for Week 1, Day 1 if performed within 7 days prior to Week 1, Day 1.
- ^k Glucose levels may be obtained by fingerstick. Screening results may be valid for Week 1, Day 1 if performed within 7 days prior to Week 1, Day 1.
- ^l Fasting lipid profile includes total cholesterol, HDL, LDL, triglycerides, amylase, and lipase. Screening results may be valid for Week 1, Day 1 if performed within 7 days prior to Week 1, Day 1.
- ^m Includes specific gravity, pH, glucose, protein, ketones, and blood. Screening results may be valid for Week 1, Day 1 if performed within 7 days prior to Week 1, Day 1.
- ⁿ Pretreatment sample for plasma protein biomarkers should be obtained prior to dosing. Refer to laboratory manual for more information.
- ^o Pretreatment sample for ctDNA may be obtained on Day 1 prior to dosing. This sample will also be collected prior to dosing at Week 9 and at Week 16. Refer to laboratory manual for more information.
- ^p Blood for NGS will be collected if allowed by local regulatory authorities and may be obtained prior to dosing on Week 1.
- ^q Blood for pharmacogenomics will be collected if allowed by local regulatory authorities and may be obtained prior to dosing on Week 1.

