Appendix 2 Schedule of Pharmacokinetic Assessments

Visit	Timepoint	PK Assessments
Day 1	3 hours post (± 60 min) letrozole and GDC-0032/placebo administration	Letrozole PK
		GDC-0032 PK
Day 15 (+ 2 days)	0–4 hours prior to letrozole and GDC-0032/placebo administration	Letrozole PK
		GDC-0032 PK
	3 hours (± 60 min) post letrozole and GDC-0032/placebo administration ECG before PK	Letrozole PK
		GDC-0032 PK
Day 57 (+/- 2 days)	3 hours post (± 60 min) letrozole and GDC-0032/placebo administration	Letrozole PK GDC-0032 PK

ECG=electrocardiogram; min=minutes; PK=pharmacokinetics.

Record exact time of dose administration and sample collection.

Appendix 3

Modified Response Evaluation Criteria in Solid Tumors: Assessment of Response of Neoadjuvant Therapy in Early Breast Cancer

Conventional response criteria may not be ideal for the assessment of response in the setting of neoadjuvant therapy in early breast cancer. Therefore, RECIST 1.1 criteria have been modified to specifically address assessment of primary breast lesions along with axillary lymph node disease, using a range of breast imaging modalities. Selected sections from the Response Evaluation Criteria in Solid Tumors (RECIST), Version 1.1¹ are presented below, with modifications and the addition of explanatory text as needed for clarity. For detailed information on the read methodology including how imaging data should be processed prior to reads, please refer to the Study Imaging Charter.

	RECIST v1.1	Modified RECIST Early Breast Cancer Neoadjuvant Therapy
Modalities	CT as primary modality, ultrasound not recommended	No CT; primary assessments by MRI; also assessments by ultrasound, mammography, and clinical exam
Lymph nodes	May be considered target lesions based on size criteria (≥ 15 mm in SAD)	Only axillary lymph nodes assessed; nodes that are considered abnormal on imaging (based on morphological factors including, but not limited to SAD) to be followed as non-target lesions
Possibility of having only non-target disease	Allowed	Not allowed; primary breast lesions must be measurable by MRI and/or ultrasound

CT = computed tomography; MRI = magnetic resonance imaging; SAD = short axis dimension.

BASELINE DOCUMENTATION OF TARGET AND NON-TARGET LESIONS

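### No fasting glucose is scheduled between Day 1 and Day 29, so asymptomatic hyperglycemia that Table 2 acts on goes untested for the first 20 of 80 doses

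*Protocol*

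**What the plan says.** Section 5.1.1.1 (Management of Hyperglycemia) provides for HbA1c and fasting glucose at baseline. For the treatment period it states that "additional monitoring of fasting glucose levels during the study will be implemented, as outlined in the schedule of assessments". Appendix 1 is therefore the only place where on-study glucose testing is fixed.

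The file holds two versions of Appendix 1, one with added DLCO and bone density rows and one without. They agree on this point: the row "Fasting insulin and glucose" is marked at screening, Weeks 1, 5, 9, 13 and 16 and post-surgery, and not at Week 3.

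Table 2 in Section 5.1.1.1 is graded on fasting blood glucose. Grade 2 calls for an anti-hyperglycemic agent and extra glucose monitoring. For asymptomatic Grade 3, "GDC-0032 dosing will be suspended and the patient will be managed as per standard of care".

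Patients do attend at Week 3, Day 15 (+2). Appendix 1 marks vital signs, ECG, tumor sampling and "GDC-0032/placebo accountability/ dispensation" at that visit. Appendix 2 adds a PK sample 0–4 "hours prior to letrozole and GDC-0032/placebo administration".

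**The concern.** Table 2 has a category of its own for asymptomatic Grade 3 hyperglycemia and requires dosing to stop. That instruction, like the Grade 2 instruction, can only be carried out if a glucose result exists. For about the first four weeks of exposure to a drug with known hyperglycemia, Appendix 1 produces no such result.

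The other safeguards do not fill this gap:

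- The entry limit on fasting glucose (125 mg/dL) and the exclusion of medicated diabetes lower baseline risk, but say nothing about the response to the drug.
- Symptom reporting and adverse event questioning at Week 3 find symptomatic cases.
- The extra monitoring in Table 2 starts only once an event is known.
- IDMC review looks at aggregate safety.

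At stake is continued dosing of an individual patient whose glucose has already reached a level at which the protocol says to treat or stop. Section 5.2.3 lists "Grade 4 hyperglycemia" and symptomatic Grade 3 or higher as events of special interest with 24-hour reporting, so finding the earlier, silent stage has a clear purpose.

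**Working it through.** The protocol states no figure for this interval, so there is none to reproduce. The check is a comparison of schedule rows followed by a calendar count.

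**Glucose-related tests in Appendix 1 (same in both versions)**

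| Test | Before first dose | Week 3 (Day 15 +2) | Week 5 (Day 29 ±2) |
|---|---|---|---|
| Fasting insulin and glucose | Screening, Day 1 | none | yes |
| Fasting serum chemistry (includes glucose) | Screening, Day 1 | none | yes |
| Urinalysis (includes glucose) | Screening | none | yes |
| HbA1c | Screening | none | none |

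Appendix 1 has assessments done before dosing unless stated otherwise, so the Day 1 value cannot show a drug effect. Its footnotes also let a screening value up to 7 days old stand in for Day 1. The nominal gap between two consecutive results can then reach 7 + 28 = 35 days.

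**Doses taken before the first on-treatment result**

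Inputs from Section 4.3.2.1: 6 mg, 5 days on and 2 days off, at most 16 weeks. With Day 1 opening a five-day block, day d (1 to 112) is a dosing day when (d − 1) mod 7 < 5.

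- Total: 16 × 5 = 80 doses; 80 × 6 = 480 mg.
- Before Day 29: 4 × 5 = 20 doses; 20/80 = 25%; 20 × 6 = 120 mg. Any 28 consecutive days contain 20 dosing days, so this does not depend on where in the block Day 1 falls.
- Across the ±2 window: 20 doses before Day 27, 28 or 29, 21 before Day 30 and 22 before Day 31. That is 26 to 30 days after Day 1.
- Before Day 15: 2 × 5 = 10 doses; 10/80 = 12.5%; 60 mg. Across the +2 window: 10 to 12 doses, 14 to 16 days after Day 1.

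**Size of the known risk**

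Section 1.7.1 reports 27 patients on GDC-0032 plus letrozole (19 at 6 mg and 8 at 9 mg, daily).

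- Related hyperglycemia 26%, consistent with 7/27 = 25.9% (exact 95% CI 11.1–46.3%).
- Grade 3-4 3.7%, consistent with 1/27 = 3.7% (exact 95% CI 0.09–19.0%).
- Weekly dose there: 7 × 6 = 42 mg or 7 × 9 = 63 mg. Here: 5 × 6 = 30 mg. Rates may therefore be lower in this trial.

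**Is Day 15 late enough to be informative?**

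Section 1.7.1.1 gives a half-life of 36.7–43.8 hours. Five half-lives are 183.5–219 hours, or 7.6–9.1 days, so accumulation should be largely complete by Day 15. Days 15 and 29 are two whole weekly cycles apart (14 = 2 × 7), so they fall at the same point of the dosing week.

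**The case against.** Nothing here is misstated. Section 5.1.1.1, Table 2 and Appendix 1 agree with one another, and testing every four weeks is a regular scheme whose later intervals are just as long. A Week 3 test matters only if silent Grade 2-3 hyperglycemia arises before Day 29, and the protocol gives neither onset times nor the share of cases without symptoms. The letrozole cohort had no dose-limiting toxicity at 6 or 9 mg daily, and the Grade 4 hyperglycemia that was dose-limiting in Phase I occurred at 16 mg. At Grade 2 the investigator may continue GDC-0032, so only asymptomatic Grade 3 makes stopping mandatory. Day 15 pre-dose may fall after two days off drug, when exposure is lowest. Investigators may also test off schedule.

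Much of this is true and limits what can be claimed: the missed cases cannot be counted, and the risk is probably below the Phase I rates. Three smaller points also stand. The window lets the Week 5 test fall on Day 27 or 28. If Day 1 were the third day of a block, 18 doses (3 + 5 + 5 + 5) would precede Day 27. The Week 3 mark in the accountability and dispensation row does not by itself prove that drug is handed out.

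None of it supplies scheduled detection of a silent case. Discretionary testing will vary across about 110 sites, whereas Table 2 presupposes a result. A delay at Grade 2 still delays the anti-hyperglycemic agent that Table 2 calls for. If Day 15 is an unfavorable point in the dosing week, Day 29 is equally so, and the protocol relies on Day 29.

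**Conclusion.** The concern holds. After the pre-dose Day 1 sample, no scheduled test can show hyperglycemia until Day 29 (±2), by which time a patient on full dosing has taken 20 of 80 doses at the nominal day. A Week 3 test would halve this to 10 doses and 14 days. The count assumes no missed or held doses. The number of patients affected is not estimated, because that would need onset times and an asymptomatic share that the protocol does not give. This is a patient-safety point about a schedule that the protocol itself fixes. It does not touch sample size, alpha or the endpoints. The change is recommended because the toxicity is known, Table 2 depends on a test result, and the visit already takes place.

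**What to change.** In Appendix 1, mark the fasting insulin and glucose row at Week 3, Day 15 (+2). Add a note that only glucose is needed, that it may be taken with the pre-dose PK sample, and that fingerstick is allowed; the existing footnote already says "Glucose levels may be obtained by fingerstick". Instruct patients to attend that visit fasting. Table 2 then applies to the result as written. Other visits, dosing and the PK schedule stay as they are.

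The cost is one table entry and one glucose test per patient at an existing visit. The real burden is fasting attendance on a day that already includes a biopsy, an ECG and PK sampling. GDC-0032 or placebo "should be taken on an empty stomach" in any case (about 1 hour before or 2 hours after a meal), which eases that burden but does not remove it.
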